5.4.3.2 Rave Specimen Tracking Process Steps

Step 1: Complete the **Histology and Disease** form (but do not upload reports until a specimen label can be applied to them) and the Baseline forms regarding **Prior Therapies**. Enter the initial clinical specimen data:

- **Specimen Tracking Enrollment CRF:** Enter Time Point, Specimen Category, Specimen Type, Block number (if applicable), Tissue type, Surgical Path ID (if applicable), and number of labels needed (include extra labels to apply to reports to be uploaded). CRF generates unique Specimen ID.

Step 2: Print labels using report in EDC and collect specimen.

- Label specimen containers and write collection date and pre-treatment/on-treatment status on each label. After collection, store labeled specimens as described in Section 5.4.2.
- Apply an extra specimen label to *each* report before scanning. Return to the **Histology and Disease** form to upload any initial Pathology, Radiology, Molecular Reports (up to 4), Surgical (or Operative) reports and Pathology Verification form (when applicable). Return to **Specimen Tracking Enrollment** CRF to upload any molecular report (one per specimen) and/or specimen specific pathology or related report (one per specimen). Uploaded reports should have protected health information (PHI) data, like name,

mailing address, medical record number or social security number (SSN), redacted. Do not redact SPID, block number or relevant dates (such as collection date), and include the UPID and patient study ID on each document.

Step 3: Complete specimen data entry.

- **Specimen Transmittal Form:** Enter collection date and pre-treatment/on-treatment status and other required specimen details.

Step 4: When ready to ship, enter shipment information.

- **Shipping Status CRF:** Enter tracking number, your contact information, recipient, number of containers and ship date once for the first specimen in a shipment.
- **Copy Shipping CRF:** Select additional specimens to add to an existing shipment referenced by the tracking number.

Step 5: Print shipping list report and prepare to ship.

- Print two copies of the shipping list, one to provide in the box, the other for your own records.
- Print pathology or other required reports to include in the box. Be sure the printed copy includes the specimen label.

Step 6: Send email notification.

- For only one of the specimens in the shipment, click “Send Email Alert” checkbox on the **Shipping Status CRF** to email recipient.

Step 7: Ship the specimen(s).

5.5 Specimen Collection

5.5.1 Formalin-Fixed Tumor Biopsies

1. Label formalin-filled containers according to instructions in Section 5.4.2.
2. Obtain 3-4 16-gauge or 18-gauge core needle biopsy specimens, and place one core in each cassette.
3. Snap the cassette lids closed and place cassettes into a formalin-filled pre-labeled container as soon as possible after collection to prevent air drying. Up to two cassettes may be placed in one formalin jar.
4. Secure the container lids and package containers into the shipping kit according to instructions in Section 5.6. Keep tissue in formalin jars at room temperature until shipment to the EET Biobank.

5.5.2 Collection of Blood in EDTA Tubes for Ambient Whole Blood Shipment

1. Label EDTA tubes according to the instructions in Section 5.4.2.
2. Collect the specified amount of blood (10 mL) in EDTA tube(s) and gently invert tube to mix.
3. Ship on day of collection (whenever possible) according to instructions in Section 5.6.

4. If blood cannot be shipped on the day of collection (e.g., a late scheduled collection), then refrigerate until shipment.

5.6 Shipping Specimens from Clinical Site to the EET Biobank

5.6.1 General Shipping Information

Core biopsies that are fixed in formalin and fresh blood should be shipped as one shipment at ambient temperature, whenever possible. The shipping container sent with kit contents should be used to ship specimens to the EET Biobank. In winter months, please include extra insulation, such as bubble wrap, inside the shipping container.

For formalin-fixed biopsies, if the corresponding anatomical pathology report is not available at the time of shipment, then the surgical and/or radiology reports from the tissue removal procedure and the diagnostic anatomic pathology report must be included in the package, or the specimen will not be processed. Once completed, upload the corresponding pathology report to the ETCTN specimen tracking system and send a copy to the EET Biobank.

5.6.2 Specimen Shipping Instructions

Tissue in formalin must be shipped on the day of collection. Collect and ship on Monday through Wednesday.

Fresh blood may be shipped on Monday through Friday. Please select “Saturday Delivery” when shipping fresh blood on a Friday.

5.6.2.1 Shipping Ambient Blood in Your Own Container

If blood and tissue are ready to ship on the same day, then the blood may be packaged and shipped in the single chamber kit with the tissue. If blood is shipped separately then it must be shipped using institutional supplies. Packaging guidelines for sending blood in a separate box are provided below.

1. Before packaging specimens, verify that each specimen is labeled according to instructions in Section 5.4.1
2. Place the blood collection tube(s) into a zip-lock bag.
3. Place zip-lock bag into a biohazard envelope with absorbent material. Expel as much air as possible and seal the envelope securely.
4. Place the biohazard envelope into a Tyvek envelope. Expel as much air as possible and seal securely.
5. Place the specimen(s) and a copy of the shipping manifest into a sturdy shipping container. In winter months, please use an insulated container and include extra insulation, such as bubble wrap, inside the shipping container to prevent specimens from freezing.
6. Close the container and tape shut.
7. Attach a shipping label to the top of the shipping container.

8. Attach an Exempt Human Specimen sticker to the side of the container.
9. Ship specimens via overnight courier to the address below. FedEx Priority Overnight is strongly recommended to prevent delays in package receipt.

5.6.2.2 Shipping Ambient Tissue and Blood in a Single-Chamber Kit

If blood and tissue are ready to ship on the same day, then the blood may be packaged and shipped in the single chamber kit with the tissue. If blood is shipped separately then it must be shipped using institutional supplies. Packaging guidelines for sending both specimens in the kit box are provided below.

1. Before packaging specimens, verify that each specimen is labeled according to the instructions above and that the lids of all primary receptacles containing liquid are tightly sealed. The lids of formalin jars should be wrapped in parafilm. Absorbent material must be placed around each primary container that holds liquid.
2. Place the specimens in zip-lock bags. Use a separate bag for each specimen type.
3. Place specimens into the secondary pressure vessel surrounded by bubble wrap. Place the lid on the secondary pressure vessel and set it inside the kit chamber.
4. Place a copy of the shipping manifest and corresponding reports such as pathology, surgical, or radiology reports into the insulated shipping container.
5. Set the lid on top of the container. Close the outer flaps and tape shut.
6. Attach a shipping label to the top of the shipping container.
7. Attach an Exempt Human Specimen sticker to the side of the container.
8. Ship specimens via overnight courier to the address below. FedEx Priority Overnight is strongly recommended to prevent delays in package receipt.

5.7 Biomarker Plan

List of Biomarker Assays in Order of Priority

Priority	Biomarker Name	Assay (CLIA: Y/N)	Use in the Trial and Purpose	Specimens Tested	Collection Time Points	Mandatory or Optional	Assay Laboratory and Lab PI
Tissue-based Biomarkers							
1	Whole Exome Sequencing in Tumor Tissue	WES CLIA: N	Integrated To evaluate the genomic landscape of chondrosarcoma tumors, including IDH1/2 mutational status. To evaluate whether IDH1/2 mutational status is related to clinical benefit from study treatment.	DNA from FFPE tumor tissue	Pre-treatment (within 21 days of C1D1) Cycle 2 Day 3, 4, or 5 (2-8 hours post dose)	M	Molecular Characterization (MoCha) Laboratory, Frederick National Laboratory for Cancer Research (FNLCR) [name].
2	RNAseq	RNAseq CLIA: N	Integrated To evaluate for changes in gene expression associated with study treatment to interrogate the mechanism of action. Specific hypotheses will be tested based upon the preclinical data.	RNA from FFPE tumor tissue	Pre-treatment (within 21 days of C1D1) Cycle 2 Day 3, 4, or 5 (2-8 hours post dose)	M	Molecular Characterization (MoCha) Laboratory, Frederick National Laboratory for Cancer Research (FNLCR) [name].

Priority	Biomarker Name	Assay (CLIA: Y/N)	Use in the Trial and Purpose	Specimens Tested	Collection Time Points	Mandatory or Optional	Assay Laboratory and Lab PI
Tissue-based Biomarkers							
3	Tumor Immune Microenvironment	Multiplex IHC using the VECTRA and inFORM platforms CLIA: N	Exploratory To evaluate effects of study treatment on the immune microenvironment using multiplex immunohistochemistry to define changes in infiltrating immune cell subsets and expression of PD-L1 and MHC by tumor and immune cells.	Unstained slides from FFPE tumor tissue core	N/A (Collected as part of the WES/ RNAseq biopsies)	O	Columbia University Medical Center Immune Monitoring Core [name]. [contact]
Blood-based Biomarkers							
1	Companion Germline Sequencing	CLIA: N	Integrated To collect a blood sample for germline WES to complement the tumor tissue WES.	DNA from Blood in EDTA	Pre-treatment (within 21 days of C1D1)	M	Molecular Characterization (MoCha) Laboratory, Frederick National Laboratory for Cancer Research (FNLCR) [name].

5.8 Integrated Correlative Studies

5.8.1 Whole Exome Sequencing in Tumor Tissue

5.8.1.1 Specimen Receipt and Processing at the EET Biobank

Tumor tissue received in formalin will be paraffin-embedded. All FFPE blocks will be sectioned to generate an initial hematoxylin and eosin (H&E)-stained slide and, for nucleic acid extractions, additional RNase-free slides. If needed, slides will be macrodissected to enrich tumor content before scraping for nucleic acid co-extraction.

DNA and RNA will be co-extracted from tumor tissue. The nucleic acids will be analyzed to determine concentration and quality. Aliquots of DNA will be shipped to the central sequencing laboratory for analysis.

DNA will be extracted from whole blood in EDTA. An aliquot of blood (germline) DNA will be shipped with the tumor DNA.

5.8.1.2 Site Performing Correlative Study

This assay will be performed at the Molecular Characterization (MoCha) Laboratory, Frederick National Laboratory for Cancer Research (FNLCR).

5.8.2 RNAseq

5.8.2.1 Specimen Receipt and Processing at the ETCTN Biorepository

Tumor tissue received in formalin will be paraffin-embedded. All FFPE blocks will be sectioned to generate an initial hematoxylin and eosin (H&E)-stained slide and, for nucleic acid extractions, additional RNase-free slides. If needed, slides will be macrodissected to enrich tumor content before scraping for nucleic acid co-extraction.

DNA and RNA will be co-extracted from tumor tissue. The nucleic acids will be analyzed to determine concentration and quality. Aliquots of RNA will be shipped to the central sequencing laboratory for analysis.

5.8.2.2 Site Performing Correlative Study

This assay will be performed at the Molecular Characterization (MoCha) Laboratory, Frederick National Laboratory for Cancer Research (FNLCR).

5.9 Exploratory/Ancillary Correlative Studies

5.9.1 Tumor Immune Microenvironment

5.9.1.1 Specimen Receipt and Processing at the EET Biobank

Tumor tissue received in formalin will be paraffin-embedded. All FFPE blocks will be sectioned to generate an initial hematoxylin and eosin (H&E)-stained slide.

Ten (10) unstained, uncharged, 4-micron, air-dried slides are created from both the baseline (pre-treatment) and on-treatment biopsies, labeled appropriately, and sent under ambient conditions by overnight courier to the Immune Monitoring Core at Columbia University.

Shipping Address

Immune Monitoring Core Facility
[name]
[name]
[name]

Contact Information for Assistance

Name: [name].
[contact]
Email: [contact]

5.9.1.2 Site Performing Correlative Study

This assay will be performed at the Columbia University Medical Center Immune Monitoring Core.

6. TREATMENT PLAN

6.1 Agent Administration

Patients Receiving Belinostat and SGI-110 (guadecitabine)

Note: Effective with Amendment 5, no further subjects will be enrolled to the belinostat

and SGI-110 (guadecitabine) regimen. Patients enrolling on the study will be treated with belinostat and ASTX727 (see Section 6.2).

Patients enrolled prior to Amendment 5 who have been receiving belinostat and SGI-110 (guadecitabine) will continue to receive that treatment regimen. SGI-110 will no longer be available from the company as of 31-AUG-2021. Further treatment options will be discussed with subjects enrolled to the belinostat/SGI-110 regimen who remain on treatment as of 31-AUG-2021. Patients may be allowed to change treatment to ASTX727 and belinostat in August 2021 if the overall assessment of risks versus benefits support that change, primarily related to any observations of adverse safety and tolerability of ASTX727 and belinostat at that time.

Treatment will be administered on an outpatient basis. Patients will be evaluated in the outpatient clinic by the treating investigator and research team on day 1 of each cycle. Patients need not be evaluated by the investigator on the other treatment days in a cycle unless clinically warranted. The study agents will be administered by qualified nursing staff consistent with institutional guidelines for administration of subcutaneous and intravenous oncology agents of these classes.

SGI-110 (guadecitabine) is given first by subcutaneous injection. At least 10 minutes, but no longer than 60 minutes, after the SGI-110 (guadecitabine) injection is completed, the belinostat infusion may begin.

There is no clinical evidence to support the sequencing of one agent prior to the other in terms of efficacy or toxicity. SGI-110 (guadecitabine) will be given first considering this agent is administered subcutaneously and may take longer to absorb than belinostat. This approach is also consistent with published combination studies with SGI-110 (guadecitabine) in solid tumors. In addition, in our preclinical studies exploring a sequential approach to treatment, efficacy appeared greater when SGI-110 (guadecitabine) was given prior to concurrent treatment as compared to giving belinostat before concurrent treatment, providing further support for this approach (Figure 8).

Reported AEs and potential risks are described in Section 10. Appropriate dose modifications are described in Section 7. No investigational or commercial agents or therapies other than those described below may be administered with the intent to treat the patient's malignancy.

The proposed study is an open-label, single-arm, Simon 2-stage phase 2 clinical trial with a safety lead-in and a continuous toxicity monitoring rule. All patients will receive SGI-110 (guadecitabine) 45 mg/m² SC in combination with belinostat 1,000 mg/m² IV over 30 minutes on Days 1-5 in 28-day cycles. Treatment will continue until a criterion for removal from the study is met (see Section 6.3 Duration of Therapy).

The belinostat and SGI-110 (guadecitabine) combination has not been previously studied and there is no defined RP2D. The FDA-approved dose of belinostat in relapsed or refractory peripheral T-cell lymphoma is 1,000 mg/m² IV on Days 1-5 of a 21-day cycle. SGI-110 (guadecitabine) is not FDA-approved. This agent was initially evaluated in a phase 1 dose

escalation study in patients with AML or MDS where the drug was administered on Days 1-5 of a 28-day cycle (Issa *et al.*, 2015). DLT related to myelosuppression was observed at 125 mg/m²; therefore, the MTD was established at 90 mg/m². Because pharmacodynamic studies demonstrated maximal biologic (demethylating) effect at 60 mg/m², the RP2D was 60 mg/m² SC on Days 1-5 of a 28-day cycle.

Although SGI-110 (guadecitabine) and belinostat have not been formally studied together, numerous published studies have evaluated various combinations of hypomethylating agents and histone deacetylase inhibitors and have found these combinations to be well tolerated. For example, in a phase 1 dose escalation study of azacitidine and belinostat in AML, no DLTs were observed at any dose level, and the RP2D was belinostat 1,000 mg/m² with azacitidine 75 mg/m² on Days 1-5 of a 28-day cycle (Odenike *et al.*, 2015). Thus, both agents were combined at their FDA-approved monotherapy doses. The most common toxicities were grade 1/2 nausea, vomiting, anorexia, and fatigue. Even in this heavily pretreated AML population, grade 3/4 hematologic events were uncommon. Similarly, in another phase 1 study in AML/MDS, decitabine and vorinostat were safe and tolerable in combination at their monotherapy doses (Kirschbaum *et al.*, 2014). Other studies evaluating azacitidine and panobinostat in myeloid malignancies and azacitidine and entinostat in both colorectal cancer and in breast cancer further support favorable tolerability of these combinations (Azad *et al.*, 2017; Connolly *et al.*, 2017).

SGI-110 (guadecitabine) has been studied as monotherapy and in combination with several other agents in solid tumors. In hepatocellular carcinoma, the RP2D as monotherapy was 45 mg/m² on Days 1-5 of a 28-day cycle. In colorectal cancer, SGI-110 (guadecitabine) was well tolerated at 45 mg/m² in combination with irinotecan with growth factor in a heavily pretreated population (Lee *et al.*, 2018). In melanoma, SGI-110 (guadecitabine) was well tolerated at 60 mg/m² in combination with checkpoint blockade (Di Giacomo *et al.*, 2019). Although a phase 1 study evaluating SGI-110 (guadecitabine) in combination with carboplatin in ovarian cancer arrived at a lower dose of SGI-110 (30 mg/m²), this study included a heavily pre-treated population in which the median number of prior treatment lines was 7 and a myelosuppressive dose of carboplatin (AUC 5) was used (Matei *et al.*, 2018).

Considering there are no FDA-approved treatments for chondrosarcoma (that is, patients will not be heavily pretreated with chemotherapy) and noting that combination studies with hypomethylating agents and HDAC inhibitors have shown favorable tolerability as discussed above, a starting dose of 45 mg/m² appears warranted. To closely monitor for unexpected adverse events, both a safety lead-in and continuous toxicity monitoring rule are applied as further described in Section 9.

Regimen Description				
Agent	Dose	Route	Schedule	Cycle Length
SGI-110 (guadecitabine)	45 mg/m ²	Slow SC injection	Days 1-5	28 days (4 weeks)
Belinostat	1,000 mg/m ²	IV over 30 (±5) min*	Days 1-5	

*May extend belinostat infusion to 3 hours if infusion-related reactions occur.

- SGI-110 (guadecitabine) is administered first, followed by belinostat. Separate SGI-110 (guadecitabine) and belinostat administration by at least 10 minutes but no more than 60 minutes.
- **Patients must receive a prophylactic 5-HT3 receptor antagonist prior to belinostat during the first two cycles of treatment – see Section 6.2.3.1.**
- **Patients must receive prophylactic use of growth factor– see Section 6.2.1.1.**

Patients Receiving Belinostat and ASTX727

Beginning with Amendment 5, subsequent patients enrolled on this study will receive treatment with belinostat and ASTX727. These patients will not receive SGI-110 (guadecitabine).

ASTX727 is an orally available DNMT inhibitor which consists of oral cedazuridine, a cytidine deaminase inhibitor, in combination with oral decitabine. ASTX727 is an oral tablet with a fixed dose combination of cedazuridine 100 mg and decitabine 35 mg. See Section 2.2.3 for additional information on ASTX727. Because ASTX727 has not been studied in combination with an HDAC inhibitor, we will repeat the safety lead-in portion of this study among the first 6 patients to receive belinostat and ASTX727. The safety lead-in and the effects of this change on study design and statistical considerations are further described in Section 9.

Treatment will be administered on an outpatient basis. Patients will be evaluated in the outpatient clinic by the treating investigator and research team on day 1 of each cycle. Patients need not be evaluated by the investigator on the other treatment days in a cycle unless clinically warranted. The study agents will be administered by qualified nursing staff consistent with institutional guidelines for administration of oral and intravenous oncology agents of these classes.

ASTX727 will be given first orally. At least 30 minutes, but no longer than 60 minutes, after ASTX727 is administered, the belinostat infusion may begin. Treatment will continue until a criterion for removal from the study is met (see Section 6.3 Duration of Therapy).

Regimen Description				
Agent	Dose	Route	Schedule	Cycle Length
ASTX727	1 tablet, which consists of cedazuridine 100 mg / decitabine 35 mg	Orally	Days 1-5	28 days (4 weeks)
Belinostat	1,000 mg/m ²	IV over 30 (±5) min*	Days 1-5	

*May extend belinostat infusion to 3 hours if infusion-related reactions occur.

- ASTX727 is administered first, followed by belinostat. Separate ASTX727 and belinostat administration by at least 30 minutes but no more than 60 minutes. Patients will be instructed to bring ASTX727 to clinic and take the medication in clinic to ensure the timeframe is observed.

- **Patients must receive a prophylactic 5-HT3 receptor antagonist prior to belinostat during the first two cycles of treatment – see Section 6.2.3.1.**
- **Patients must receive prophylactic use of growth factor– see Section 6.2.2.1.**

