1.2 Secondary Objectives

- 1.2.1 To evaluate the toxicity profile associated with belinostat and ASTX727.
- 1.2.2 To evaluate the progression free survival (PFS) associated with belinostat and ASTX727.
- 1.2.3 To evaluate the toxicity profile, objective response rate and progression free survival among the initial six patients treated with belinostat and SGI-110 (guadecitabine) prior to Amendment 5 in which ASTX727 was substituted for SGI-110 (guadecitabine).

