9. STATISTICAL CONSIDERATIONS

The proposed study is an open-label, single-arm, Simon 2-stage phase 2 clinical trial. Neither

the combination of belinostat and SGI-110 (guadecitabine) nor the combination of belinostat and ASTX727 have been formally evaluated in a phase 1 dose-finding study and therefore a safety lead-in and continuous safety monitoring rule will be applied to monitor for excessive or unexpected toxicity as described in this section.

There is no approved or accepted standard therapy for CS. Chemotherapy is generally ineffective, and no drug has shown clinical efficacy to date. Conventional CS patients are commonly enrolled on clinical trials in the first-line setting. Although chemotherapy is sometimes employed, efficacy is marginal and toxicity is significant. We expect that many sarcoma oncologists would find a chemotherapy control arm problematic, and this would create a barrier to accrual. For these reasons, a single-arm (non-randomized) design is proposed in this rare disease.

With Amendment 5, the study was modified to substitute ASTX727 for SGI-110 (guadecitabine). These are similar agents with the same mechanism of action. At the time of this modification, 6 patients were enrolled and treated with belinostat and SGI-110 (guadecitabine). We will report safety and efficacy endpoints separately for these 6 patients. These 6 patients will be replaced for the purposes of the original study design. The Simon 2-stage design described below will be conducted among patients treated with belinostat and ASTX727. A new safety lead-in will be performed among the first 6 patients treated with belinostat and ASTX727. The continuous toxicity monitoring rule will also apply. The total sample size for the study will increase from 26 patients to 32 patients, accounting for the 6 patients that will be replaced.

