9.1.2 Secondary Endpoints

Secondary endpoints are the presence of treatment related AEs, the occurrence of DLTs, and PFS. Adverse events will be recorded at each clinical visit and will be categorized according to NCI CTCAE version 5.0. The attribution of AEs to each of the study drugs will also be recorded.

Secondary endpoints will be reported separately for the population of patients receiving belinostat and SGI-110 (guadecitabine) and the population of patients receiving belinostat and ASTX727.

The study will use a continuous toxicity monitoring rule as described in Section 9.4. DLTs are defined in Section 9.2 and to qualify as DLT must be attributed to the study drugs and not to disease, and occur (or first become evident) during the first four cycles of treatment for the purposes of continuous toxicity monitoring.

PFS is defined as the time from first treatment with the study drug to the earliest of either disease progression or death from any cause. Patients who are alive and progression free will be censored at the time of their last follow-up.

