9.4 Continuous Toxicity Monitoring Rule

In addition to the safety lead-in, a continuous toxicity monitoring rule will be applied to this study to monitor for excessive or unexpected toxicity associated with study treatment (Ivanova *et al.*, 2005). Patients will be subjected to continuous toxicity monitoring during the first four cycles of study treatment. Sequential boundaries will be used to monitor the DLT rate. DLTs are defined in Section 9.2 above. According to this model, shown in the table below, enrollment will be halted if the number of DLTs is equal to or exceeds b_n out of n patients with completed DLT follow-up. This is a Pocock-type stopping boundary which yields a probability of crossing the boundary (early stopping) of at most 30% stopping when the rate of DLT is equal to the acceptable rate of 20% using a pre-defined sample size of 26 patients. This boundary is equivalent to testing the null hypothesis, after each patient, that the event rate is equal to 0.20, using a one-sided level 0.14 test.

With Amendment 5, the study was modified to substitute ASTX727 for SGI-110 (guadecitabine). The continuous toxicity monitoring rule will apply as defined above to patients treated with belinostat and ASTX727. Toxicities experienced by the initial cohort of 6 patients treated with SGI-110 (guadecitabine) and belinostat will not be considered in the model as it

applies to subsequent patients treated with ASTX727 and belinostat.

If the early stopping event occurs, the study will be halted and the investigators, CTEP, and the DSMB (if applicable) will discuss whether to close the study early for toxicity or modify the protocol to address the observed events. In addition, if any grade 5 event at least possibly related to study treatment occurs, the study will also be halted for review in this fashion.

Number of patients (n)	1	2	3	4	5	6	7	8	9	10	11	12	13
Boundary, b_n	-	2	2	3	3	3	4	4	4	4	5	5	5
Number of patients (n)	14	15	16	17	18	19	20	21	22	23	24	25	26
Boundary, b_n	5	6	6	6	6	7	7	7	7	8	8	8	8

Investigators are expected to report any DLT events directly to the study statistician and the Data Coordinating Center within 24 hours of their knowledge of such an event.

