9.6.2 Evaluation of Response

PFS is defined as the time from first treatment with the study drug to the earliest of either disease progression or death from any cause. Patients who are alive and progression-free will be censored at the time of their last follow-up. The Kaplan-Meier method will be used to evaluate time to event endpoints. Median PFS will be reported with a 95% confidence interval. Data will be presented as Kaplan Meier plots.

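### SGI-110 patients may change to ASTX727, but the separately reported SGI-110 outcomes have no cut at the change, and the ASTX727 lead-in does not expressly exclude switchers

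*Combined protocol and SAP*

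**What the plan says.** **The switch.** Section 6.1 stops enrolment to belinostat/SGI-110 with Amendment 5 and keeps patients already enrolled on that regimen. For those still on treatment when SGI-110 supply ends, it adds: "Patients may be allowed to change treatment to ASTX727 and belinostat in August 2021". The change depends on an overall risk-benefit assessment. Sections 6.1.1.1 and 8.1.1 repeat the provision.

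**The cohort.** Objective 1.2.3 covers the toxicity profile, "objective response rate and progression free survival among the initial six patients treated with belinostat and SGI-110 (guadecitabine) prior to Amendment 5". The introduction to Section 9 says: "We will report safety and efficacy endpoints separately for these 6 patients". Section 9.1.1 says the same and replaces the six for the Simon design. Section 9.1.2 splits secondary endpoints by the population of patients receiving each regimen.

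**The endpoint rules.**
- PFS (9.1.2, repeated in 9.6.2): "PFS is defined as the time from first treatment with the study drug to the earliest of either disease progression or death" from any cause. The only censoring is at last follow-up, for patients alive and progression-free. Section 12.1.6 agrees.
- Best overall response (12.1.4.3) covers the period from start of treatment to progression or recurrence.
- Toxicity evaluability (9.8.1, 12.1.1) starts at first dose and has no stated end at a change of agent. The tables in 9.6.1 count treatment-related events by type and grade, without a split by agent or period.

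**What is already protected.** Section 9.5 keeps the six out of the Simon two-stage count. Section 9.4 says: "Toxicities experienced by the initial cohort of 6 patients treated with SGI-110 (guadecitabine) and belinostat will not be considered in the model" applied to later ASTX727 patients.

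**The concern.** The plan allows a within-patient change of hypomethylating agent in one small cohort, then reports that cohort as the SGI-110 experience under rules that do not mention the change. Progression ends therapy under Section 6.3, so a switcher would ordinarily be progression-free and still able to contribute PFS time, a first response and new adverse events, all while taking ASTX727. Under the written rules these become SGI-110 results.

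What is at stake is the interpretation of objective 1.2.3. It is descriptive, but it is the only place where the SGI-110 combination is reported. A second, smaller issue is membership of the ASTX727 group. Sections 9 and 9.3 define the repeated lead-in as the first six patients treated with ASTX727 and belinostat. A switcher could fit those words, although already treated with belinostat and a related agent. The wording of 9.1.2 also fits a switcher under both regimens.

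**Working it through.** The plan states no figure on this point, so the check is of each rule against a hypothetical switcher, followed by sizing.

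**Step 1. Apply each rule to a patient who starts on SGI-110, is progression-free, and changes to ASTX727.**

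| Rule | Stops or splits at the change? | Consequence |
|---|---|---|
| PFS (9.1.2, 9.6.2, 12.1.6) | No | Time on ASTX727 counts in SGI-110 PFS |
| Best response (12.1.4.3) | No | A response first seen on ASTX727 counts for SGI-110 |
| Toxicity evaluability and tables (9.8.1, 12.1.1, 9.6.1) | No | ASTX727 events enter the SGI-110 table |
| Simon design (9.5) | The six are excluded | Protected |
| Continuous toxicity boundary (9.4) | Toxicities of the six are excluded | Protected |
| ASTX727 lead-in (9, 9.3) | Not stated | A switcher is not expressly excluded |

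**Step 2. Response rate.** With n = 6, each response first seen after a switch adds 1/6 = 16.7 points. The exact (Clopper-Pearson) 95% limits for x responses are the 2.5% point of Beta(x, 7 − x) and the 97.5% point of Beta(x + 1, 6 − x).
- x = 0: 0%, interval 0 to 45.9% (upper limit 1 − 0.025^(1/6) = 0.459)
- x = 1: 16.7%, interval 0.4 to 64.1%
- x = 2: 33.3%, interval 4.3 to 77.7%

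**Step 3. PFS, on assumed data.** The documents give no event times, number of switchers or time on study at the switch. Assume progression at 2, 2, 4, 6, 12 and 14 months and, for simplicity, a switch at the same study month for everyone still on treatment. Uncut, follow-up is 2 + 2 + 4 + 6 + 12 + 14 = 40 patient-months. Survival reaches 3/6 at month 4, so the median is 4 months.

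| Assumed switch month | Switchers | Follow-up before switch | Follow-up after switch | Median, censored at switch |
|---|---|---|---|---|
| 3 | 4 | 2 + 2 + 4×3 = 16 | 24 | not reached |
| 5 | 3 | 2 + 2 + 4 + 3×5 = 23 | 17 | 4 |
| 8 | 2 | 2 + 2 + 4 + 6 + 2×8 = 30 | 10 | 4 |

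In these scenarios 10 to 24 of the 40 patient-months credited to SGI-110 (25% to 60%) would follow the switch. The median is unchanged or not reached after the cut; it never falls. With no switchers, both versions coincide.

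**The case against.** **The cohort is defined by starting regimen.** Objective 1.2.3 refers to the initial six patients, and Section 6.1 describes the ASTX727 group as later enrollees who will not receive SGI-110. Following patients by initial regimen to progression is a legitimate estimand. This stands, and it largely settles where a switcher belongs for secondary endpoints. It does not tell the reader that the reported results may include time on another agent, and it does not settle the lead-in wording.

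**Adverse events can be separated.** Section 9.1.2 records attribution to each study drug, and Section 10.3.1 collects events by reporting period. So the information is not lost; the planned tables simply do not call for the split. PFS and response have no comparable provision.

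**The effect is conditional and confined.** The change was only permitted, in a single month, and the cohort is a six-patient description with wide intervals either way. This stands and limits the weight of the point.

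**Stronger readings that a reader might infer.**
- *Switching inflates SGI-110 PFS because switchers are the longest progression-free patients.* The switch falls at a calendar date and entry was staggered: at the planned one to two patients per month (9.5), six patients enter over about 6/2 = 3 to 6/1 = 6 months. A late entrant could be on treatment in August 2021 with short follow-up, after an earlier entrant with longer PFS had progressed. Inflation would also require ASTX727 to do better than continued SGI-110. The documents offer no such evidence, and Section 9 calls the agents similar.
- *The primary analysis or the toxicity stopping boundary is contaminated.* Sections 9.5 and 9.4 exclude the six.
- *PFS censored at the switch is the right primary version.* Only patients still on treatment can switch, so that censoring may be informative.

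**Conclusion.** The gap is real and narrow. If at least one of the six changed to ASTX727, the results reported under objective 1.2.3 would mix the two agents for PFS, response and adverse events. The direction is unknown. The size is 16.7 points of response rate for each post-switch response, plus whatever PFS time and events follow the change. If nobody switched, the size is zero. The conclusion rests on the written endpoint rules and on no assumption about how many switched; the patient-month figures are illustrations on assumed times.

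The Simon test and the continuous toxicity boundary are not affected. The lead-in wording in Sections 9 and 9.3 leaves an opening that should be closed. Separately, Section 6.3 lists the manufacturer's inability to supply the agent as a reason to end therapy, while Section 6.1 allows a change of agent in that situation. The two must be reconciled because together they determine when SGI-110 exposure ends.

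**What to change.** The current version is dated March 2025, after the August 2021 window, so who switched should now be ascertainable. If nobody did, one sentence saying so closes the reporting issue. Otherwise:

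- **9.1.2 and 9.6, reporting.** Give the number of SGI-110 patients who changed to ASTX727 and the dates. Report response rate and PFS by initial regimen, labelled as including any ASTX727 time. Beside these, report outcomes up to the first ASTX727 dose: PFS censored at that point and best response from earlier assessments. Both versions are descriptive.
- **9.6.1, toxicity.** For this cohort, tabulate adverse events by the hypomethylating agent being taken at onset.
- **9.1.2 and 9.3, populations.** State that patients who began on SGI-110 do not enter the ASTX727 lead-in or the ASTX727 secondary-endpoint population.
- **6.1 and 6.3.** Reconcile the supply-loss criterion with the switch provision.

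The cost is a few sentences and a few extra lines of descriptive output. Attribution by drug and collection by reporting period are already planned, and the Appendix F diary asks for the date of each ASTX727 tablet. The drawback is that pre-switch PFS has earlier, possibly informative, censoring, so it should not be shown alone.
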